5.7. Multiple Assessments and Visit Windows

If there are multiple assessments at a scheduled visit, then the last assessment will be used in the analysis.

Nominal visits (e.g., those identified by the study eCRF) will be the basis of summarization and statistical analysis; visit windows for each scheduled visit can be found in the Schedule of Activities from the protocol. Unscheduled data may be included in summaries of baseline and maximum/minimum change values; summaries of specific abnormalities any time post-baseline; and patient data listings.

Sponsor: Boston Pharmaceuticals, Inc.
Protocol Number: BOS-589-201
Version and Date: Version 1.2 12NOV2020

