9. SAFETY

Unless otherwise specified, all safety analysis reporting will be based on the SAF Analysis Dataset. For safety analyses, Day 29 represents measures taken at end of treatment/early termination while Day 43 represents measures taken at the end of study.

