9.2. Clinical Laboratory Evaluations

Laboratory tests identified in Appendix 1 in the protocol will be performed at times defined in the Schedule of Activities, Section 1.3 of the protocol. Clinical chemistry, hematology, and coagulation parameters will be reported based on the International System of Units (SI). All abnormal laboratory results will be evaluated by the Investigator as either clinically significant or not clinically significant.

Observed values and changes from baseline for hematology, clinical chemistry, urinalysis, and inflammatory biomarker laboratory evaluations will be summarized by cohort at each scheduled visit (Baseline/Day 1, Day 15, Day 29/Early Termination, and Day 43/End of Study) and most extreme change.

Box plots will be produced by visit and treatment for the recorded values of Erythrocyte Sedimentation Rate, C-reactive Protein, and Fecal Calprotectin. As well, line plots of the mean change from baseline of these three tests at each visit will be produced by treatment.

The number and percentage of patients experiencing treatment-emergent graded toxicities will be summarized by cohort and severity grade per the National Cancer Institute Common Terminology Criteria for Adverse Events (CTCAE) version 4.0.3. For each parameter, a patient will only be counted once using the worst-case value among all post-baseline timepoints. Laboratory toxicity will be summarized by incidence of CTCAE grade 3 and CTCAE grade 4 values for measures with a corresponding CTCAE grade. For measures without a corresponding CTCAE grade, incidence of 2.5 to < 5.0 X upper or lower limit of normal and ≥ 5.0 X upper or lower limit of normal cohort by cohort. Patients with missing values post-baseline will be excluded from the summary. The denominator for percentages will be the number of patients with at least one post-baseline assessment for the laboratory parameter being displayed. Separate summary counts will be prepared for parameters with bi-directional toxicity grading with “high/hyper” conditions depending on the maximum post-baseline value and the “low/hypo” conditions depending on the minimum post-baseline value.

All laboratory parameters will be provided in patient data listings for all enrolled patients.

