9.3. Other Safety Evaluations

For electrocardiogram and vital signs results, Marked Abnormality will be defined in the following sections. Should a patient have a Markedly Abnormal result at baseline, only those

Sponsor: Boston Pharmaceuticals, Inc.
Protocol Number: BOS-589-201
Version and Date: Version 1.2 12NOV2020

post-baseline results that are at least 1 grade more extreme than the baseline grade will be considered as a Marked Abnormality.

9.3.1. 12-Lead Electrocardiogram

12-lead electrocardiograms (ECGs) will be assessed as specified in the Schedule of Activities in Section 1.3 of the protocol. The following ECG parameters will be collected: PR interval (milliseconds [msec]), QRS interval (msec), QT interval (msec), QT interval corrected for heart rate (QTc) (msec), and Ventricular Rate (beats/min). ECG parameters and ECG evaluation will come directly from the database and will not be calculated during analysis.

Observed values and changes from baseline for ECG parameters will be summarized at each scheduled visit (Screening and Day 29/ Early Termination) by cohort and overall.

Observed and change from baseline values on Day 29 in QTc status categorized as markedly abnormal (defined in the table below) or not will be summarized.

QTc Measure	Markedly Abnormal Criteria
Observed	450–480 msec, inclusive [CTCAE grade 1] 481–500 msec, inclusive [CTCAE grade 2] > 500 msec [CTCAE grade 3 or higher]
Change from Baseline	31–60 msec, inclusive, increase from baseline >60 msec increase from baseline

If triplicate measures were taken at a single time point, the average will be summarized. All ECG data will be presented in a by patient data listing for all enrolled patients. Measures meeting the markedly abnormal criteria will be flagged in the listing.

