9.3.3. Vital Signs

Vital signs include: pulse rate (beats/min), respiratory rate (breaths/min); temperature (degrees Celsius [°C]); systolic and diastolic blood pressure (millimeters of mercury [mmHg]); height, weight (kg), and BMI (derived).

Observed values and changes from baseline for vital signs will be summarized at by cohort and overall for each scheduled visit (Baseline/Day 1, Day 8, Day 15, Day 22, Day 29, and Day 43) and most extreme change.

Summaries of pulse rate, temperature, systolic blood pressure, and diastolic blood pressure will be based on markedly abnormal criteria defined below:

Vital Sign	Markedly Abnormal Criteria
Pulse rate (beats/min)	< 60 beats/min ≥ 100 beats/min
Temperature (°C)	≤ 35 °C ≥ 38 °C
Systolic blood pressure (mmHg)	120-139 mmHg, inclusive (CTCAE grade 1) 140–159 mmHg, inclusive (CTCAE grade 2) ≥ 160 mmHg (CTCAE Grade 3)
Diastolic blood pressure (mmHg)	80–89 mmHg, inclusive (CTCAE grade 1) 90–99 mmHg, inclusive (CTCAE grade 2) ≥ 100 mmHg (CTCAE grade 3)

Incidence of post-baseline markedly abnormal worst-case values will be presented. For pulse rate and temperature, both high and low values will be presented separately such that patients can be counted in both categories.

All vital signs data will be presented in patient data listings for all enrolled patients. Markedly abnormal vital sign values will be flagged as such in the vital signs listing.

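### SAP 9.3.1 counts markedly abnormal QTc only at Day 29/Early Termination, not at the worst post-baseline value as the laboratory and vital-sign tables do, so unscheduled and superseded ECG readings have no place in the cohort count

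*SAP*

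**What the plan says.** The Protocol's Schedule of Activities (section 1.3) places ECGs at Screening and at Day 29/Early Termination only, with dosing from Day 1 to Day 28. SAP 9.3.1 summarises ECG values at those two visits and then specifies the categorical output as "Observed and change from baseline values on Day 29 in QTc status categorized as markedly abnormal (defined in the table below) or not". The criteria table beneath it has three observed bands (450–480, 481–500 and above 500 msec) and two bands of increase from baseline (31–60 and above 60 msec). SAP section 9 adds: "For safety analyses, Day 29 represents measures taken at end of treatment/early termination".

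The other two safety tables follow a different rule. For laboratory toxicity, SAP 9.2 says "a patient will only be counted once using the worst-case value among all post-baseline timepoints". For vital signs, SAP 9.3.3 says "Incidence of post-baseline markedly abnormal worst-case values will be presented".

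The general rule in SAP 5.7 is permissive: "Unscheduled data may be included in summaries of baseline and maximum/minimum change values; summaries of specific abnormalities any time post-baseline; and patient data listings". The same section says that when a scheduled visit has several assessments, the last one is analysed.

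**The concern.** ECGs recorded during dosing are the ones best placed to show an effect while the patient is on drug, and under this schedule almost all of them would be unscheduled. A table fixed at Day 29/Early Termination has no row for them. If a patient's QTc was prolonged on an unscheduled ECG and had recovered by the visit, the table would show that patient as not markedly abnormal.

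Safety relative to placebo is a primary objective and there is no safety monitoring committee, so the end-of-study cohort tables carry weight. The SAP gives no reason for treating QTc differently from laboratory values and vital signs.

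**Working it through.** The plan gives no figure to reproduce. The check compares the rules and asks when they would give different tables.

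| Assessment | Scheduled post-baseline visits | Number | Value used in the abnormality table | Most extreme change also summarised? |
|---|---|---|---|---|
| Laboratory (SAP 9.2) | Days 15, 29/ET, 43 | 3 | worst post-baseline | yes |
| Vital signs (SAP 9.3.3) | Days 8, 15, 22, 29, 43 | 5 | worst post-baseline | yes |
| QTc (SAP 9.3.1) | Day 29/ET | 1 | value at Day 29/ET | no |

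**Step 1: scheduled data only.** With one scheduled post-baseline ECG, the worst scheduled value is the Day 29/ET value. The two rules give the same table.

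**Step 2: where the rules differ.** Let S be the Day 29/ET value that is analysed and U any other QTc value after first dose. The worst-value rule uses max(S, U) and SAP 9.3.1 uses S. They differ only if U exists and either falls in a higher category than S or S is missing. There are three such cases.

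- *Unscheduled ECG during dosing.* The Day 29 visit has a window of ±1 day, so it falls on Days 28 to 30. For a patient who completes treatment on schedule, the scheduled ECG can coincide with only one of the 28 dosing days, Day 28. An ECG on any earlier dosing day is unscheduled.
- *Repeat at the visit.* Protocol 8.4.4 plans single ECGs. If a first reading above 500 msec is repeated and the repeat is below 450 msec, the last-assessment rule of SAP 5.7 keeps only the repeat. SAP 9.3.1 averages triplicates at one time point, but that does not cover a later repeat.
- *No Day 29/ET ECG.* SAP 5.8 does not impute missing evaluations, and SAP section 4 bases percentages on non-missing values. A patient with a prolonged unscheduled ECG and no Day 29/ET ECG drops out of the percentage.

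**Step 3: whether another section closes the gap.** SAP 5.7 permits unscheduled data in two kinds of summary: maximum/minimum change, and abnormalities at any time post-baseline. SAP 9.3.1 orders neither for ECG. SAP 5.5 defines maximum change over scheduled and unscheduled on-treatment values, but 9.3.1 does not call for it. A programmer following 9.3.1 would produce a table of Day 29/ET values.

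**Step 4: weight of one patient.** With 44 patients planned per cohort, 1/44 = 2.3%. If that patient's only abnormal reading is outside the table, the cohort shows 0/44 = 0%. This is an illustration and does not forecast how often it will happen.

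**The case against.** The strongest reply is that the clinically important cases are already covered. Protocol 8.4.4 has any clinically significant change in ECG interpretation recorded as an adverse event, and SAP 9.1 summarises treatment-emergent events by cohort. All ECG data are listed with markedly abnormal values flagged, and early-termination ECGs already count as Day 29. The contrast with laboratory values and vital signs also partly reflects the schedule: three and five post-baseline visits need a worst-value rule, and one does not.

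Much of this stands, and it rules out three stronger readings that a reader might infer.

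- *That an unscheduled prolonged QTc is never counted.* It is flagged in the listing, and if clinically significant it reaches the cohort adverse-event tables. What remains is narrower: a listing gives no count by cohort, and the adverse-event route depends on the investigator's judgement and does not report the QTc category.
- *That SAP 9.3.1 overrides SAP 5.7.* The SAP sets no order of precedence between them. Section 5.7 is optional and 9.3.1 does not invoke it, so the text does not amount to an explicit exclusion.
- *That 450 msec and above 500 msec are merged into one class.* The sentence can be read as a yes/no split, but the criteria table defines grades and SAP 9.3 uses them to judge worsening from baseline. The layout is in mock shells held separately, so the documents do not settle this.

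A further objection is that for-cause ECGs are not taken equally across patients, so an incidence that includes them is not a like-for-like comparison. That is a real limitation. It is a reason to keep the Day 29 summary beside the new table.

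**Conclusion.** The point holds as a modest gap in the safety tables. The QTc categorical table is defined at Day 29/Early Termination only. Unlike the laboratory and vital-sign tables, it does not use the worst post-baseline value, so an unscheduled ECG during dosing or a prolonged reading followed by a normal repeat has no place in the cohort count. The difference is confined to patients who have such an ECG. The documents give no expected number, so the size cannot be estimated beyond the weight of one patient, 2.3 percentage points in a cohort of 44. The conclusion assumes that 9.3.1 is programmed as worded and that the mock shells, which are not available here, do not already specify a worst-value table. It is a cheap improvement and does not undermine the safety analysis.

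**What to change.** Keep the Day 29 by-visit summary and add to SAP 9.3.1:

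> The number and percentage of patients in each observed QTc category (450–480, 481–500, >500 msec) and each change category (31–60, >60 msec) will be presented by cohort for the worst value after first dose through the Day 29/Early Termination visit, scheduled or unscheduled. Triplicates at one time point are averaged first; for this table the last-assessment rule of Section 5.7 does not apply; the baseline-grade rule of Section 9.3 applies.

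The second sentence is needed because a bare worst-value rule would conflict with the triplicate averaging in 9.3.1 and the last-assessment rule in 5.7, and would leave the baseline-grade rule unaddressed. The denominator should also be stated; patients with at least one QTc value in that window would match the laboratory rule in SAP 9.2.

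The cost is this short addition and a small programming change, with no extra ECGs and no protocol amendment. A table note should say that for-cause ECGs are not taken equally in all patients and that the table is to be read with the Day 29 summary.

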9.3.2. Physical Examinations

Physical examinations will be presented in patient data listings on all enrolled patients.

9.3.3. Vital Signs

Vital signs include: pulse rate (beats/min), respiratory rate (breaths/min); temperature (degrees Celsius [°C]); systolic and diastolic blood pressure (millimeters of mercury [mmHg]); height, weight (kg), and BMI (derived).

Observed values and changes from baseline for vital signs will be summarized at by cohort and overall for each scheduled visit (Baseline/Day 1, Day 8, Day 15, Day 22, Day 29, and Day 43) and most extreme change.

Summaries of pulse rate, temperature, systolic blood pressure, and diastolic blood pressure will be based on markedly abnormal criteria defined below:

Vital Sign	Markedly Abnormal Criteria
Pulse rate (beats/min)	< 60 beats/min ≥ 100 beats/min
Temperature (°C)	≤ 35 °C ≥ 38 °C
Systolic blood pressure (mmHg)	120-139 mmHg, inclusive (CTCAE grade 1) 140–159 mmHg, inclusive (CTCAE grade 2) ≥ 160 mmHg (CTCAE Grade 3)
Diastolic blood pressure (mmHg)	80–89 mmHg, inclusive (CTCAE grade 1) 90–99 mmHg, inclusive (CTCAE grade 2) ≥ 100 mmHg (CTCAE grade 3)

Incidence of post-baseline markedly abnormal worst-case values will be presented. For pulse rate and temperature, both high and low values will be presented separately such that patients can be counted in both categories.

All vital signs data will be presented in patient data listings for all enrolled patients. Markedly abnormal vital sign values will be flagged as such in the vital signs listing.

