5.5. Baseline and Post-Baseline Changes

Unless stated otherwise, baseline and post-baseline change values will be based on the following:

Sponsor: Boston Pharmaceuticals, Inc.
Protocol Number: BOS-589-201
Version and Date: Version 1.2 12NOV2020

- Baseline will be based on the last non-missing value (including unscheduled assessments) collected prior to or on the treatment start date/time for measures collected prior to the treatment.
- Post-baseline values will be those collected after the date/time of first dose of study drug.
- Change from baseline is defined as: value – baseline value.
- Percentage change from baseline is defined as: $(\text{value} - \text{baseline value}) / \text{baseline value} \times 100\%$.
- Maximum change will be based on the change from baseline value to the maximum value for all post-baseline assessments collected during the on-treatment period, scheduled or unscheduled, using the formulas above.
- Minimum change will be based on the change from baseline value to the minimum value for all post-baseline assessments collected during the on-treatment period, scheduled or unscheduled, using the formulas above.

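### The SAP's blood-pressure abnormality criteria are high-side only, so the incidence table and listing flag cannot show low pressure, although pulse and temperature are counted in both directions

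*SAP*

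**What the plan says.** SAP 9.3.3 tabulates markedly abnormal criteria for four vital signs. Pulse rate and temperature each have a low and a high limit, and the text adds: "For pulse rate and temperature, both high and low values will be presented separately such that patients can be counted in both categories". Systolic pressure has three bands, with lower edges at 120, 140 and 160 mmHg; the first is given as "120-139 mmHg, inclusive (CTCAE grade 1". Diastolic pressure has three bands, with lower edges at 80, 90 and 100 mmHg, the first being "80–89 mmHg, inclusive (CTCAE grade 1". Neither has a low limit.

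The counting rule is "Incidence of post-baseline markedly abnormal worst-case values will be presented". The scheduled vital-sign visits after baseline are Days 8, 15, 22, 29 and 43. SAP 9.3 adds an exemption for patients who already meet a criterion at baseline: only "post-baseline results that are at least 1 grade more extreme than the baseline grade will be considered as a Marked Abnormality". Listing values are flagged by the same criteria.

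Other blood-pressure output is also planned. "Observed values and changes from baseline for vital signs will be summarized at by cohort and overall for each scheduled visit", with the visits given as "Baseline/Day 1, Day 8, Day 15, Day 22, Day 29, and Day 43) and most extreme change". SAP 5.5 defines both directions of change; for the low side, "Minimum change will be based on the change from baseline value to the minimum value for all post-baseline assessments". That definition is limited to the on-treatment period. Protocol 8.4.3 has clinically significant abnormal vital signs recorded as adverse events, and SAP 9.1 tabulates treatment-emergent events by cohort.

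**The concern.** The same table treats two vital signs as two-sided and blood pressure as one-sided, and gives no reason. Read literally, a patient who goes from 118 to 121 mmHg systolic at one visit enters the table, while a patient who records 80/40 does not. Because the worst of five visits is used, ordinary visit-to-visit variation puts many patients in the table with no drug effect at all.

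Safety and tolerability is a primary objective, and SAP 3.5 states that no safety monitoring committee reviews the data. A categorical display of blood pressure should let a reader compare the cohorts in both directions. This one is insensitive to a fall, and its count moves the wrong way if pressure falls.

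**Working it through.** **What follows from the wording alone.** Let g(x) be the number of cut-offs that a reading x reaches (systolic 120, 140, 160; diastolic 80, 90, 100). A patient is flagged when the largest g over the five post-baseline readings exceeds g at baseline.

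- 118 at baseline gives g = 0, and one reading of 121 gives g = 1. Since 1 > 0, the patient is flagged.
- A reading of 80/40 gives g = 0 on both measures, so it can never be flagged.
- If every post-baseline reading is lowered by the same amount, each g stays the same or falls, so the flagged count can only stay the same or fall. This needs no assumption about the distribution.

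**How large.** The plan states no expected flag rate and no blood-pressure mean or SD, so there is no figure to reproduce. The rule was simulated with these inputs.

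- From the documents: the cut-offs, the baseline exemption, five post-baseline visits, 44 patients per cohort, and exclusion of patients above 180 systolic or 100 diastolic (Protocol 5.2).
- Assumed, not in the documents: normally distributed readings with the means and SDs shown, systolic-diastolic correlation 0.6 between patients and 0.5 within a visit, readings rounded to 1 mmHg, and 200,000 patients per scenario. The fall is a constant 10 mmHg systolic and 6 mmHg diastolic. The 90 mmHg line is for illustration only.

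| Assumed mean / between SD / within SD: systolic; diastolic | Systolic flagged: no effect → fall | Diastolic flagged: no effect → fall | Any systolic < 90: no effect → fall |
|---|---|---|---|
| 118/12/5; 74/8/4 | 26.1% → 2.9% | 27.2% → 5.0% | 3.5% → 15.5% |
| 118/12/8; 74/8/6 | 40.2% → 11.9% | 39.5% → 13.9% | 7.1% → 24.4% |
| 122/13/5; 76/8/4 | 27.7% → 3.4% | 31.5% → 6.3% | 2.4% → 10.8% |
| 122/13/8; 76/8/6 | 42.6% → 13.5% | 44.3% → 16.8% | 5.0% → 17.6% |
| 125/14/10; 78/9/7 | 50.9% → 22.5% | 52.1% → 25.2% | 6.4% → 19.0% |

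With no drug effect, 26% to 52% of patients are flagged per measure. In a cohort of 44 that is 0.26 × 44 ≈ 11 to 0.52 × 44 ≈ 23 patients. In every scenario the fall lowers the flagged share and raises the share with a systolic reading below 90.

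A separate systolic-only run of the 122/13/8 case gave 42.3% with no effect, 25.8% after a 5 mmHg fall and 13.4% after a 10 mmHg fall. Any reading below 90 went from 5.1% to 9.8% and then 17.4%.

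**Source of the high flag rate.** In a systolic-only run at mean 130, SDs 13 and 9, 49.5% are flagged: 33.4 points with a worst value of grade 2 or higher and 16.1 points at grade 1. The 120 mmHg starting point is therefore only part of the reason; taking the worst of five visits matters as well.

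**The case against.** The strongest case against is that low pressure has other routes into the report. A clinically significant low value is to be recorded as an adverse event and would then be counted in the treatment-emergent tables by cohort. By-visit changes, most extreme change and the full listings would also show a fall. The primary safety endpoint is the incidence of adverse events, not this table, which is neither tested nor tied to any decision. All of this stands.

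A reader might therefore infer too much in four ways.

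- **That hypotension is never counted, or that a pressure-lowering drug would look safer than placebo overall.** The documents support this only for the incidence table and the listing flag. The other routes remain, although the adverse-event route depends on investigator judgement, and SAP 9.3.3 does not say in which direction most extreme change is shown.
- **That nearly half of undrugged patients are flagged.** This depends on the assumed within-patient SD. Protocol 8.4.3 specifies supine readings after 5 minutes' rest, so a small SD is plausible. At an SD of 5 the systolic rate is 26% to 30% over means of 118 to 130.
- **That grade 1 should be removed from the criteria.** This is a preference. The QTc table in SAP 9.3.1 also starts at grade 1, and the mock shells, a separate document, may already show the grades in separate rows.
- **That the drug is expected to lower pressure.** Protocol 2.2.3.2 reports no drug-related clinically significant vital-sign changes in the healthy-volunteer study. The fall used above is hypothetical. That study's repeat dosing lasted 14 days, and this trial is the first use in patients with IBS-D, for 4 weeks.

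**Conclusion.** The point holds as a gap in one display. As written, the blood-pressure incidence table and listing flag in SAP 9.3.3 cannot show low pressure, and a general fall would reduce the flagged count. Both statements follow from the criteria and need no assumption. The size does rest on assumed distributions: roughly a quarter to a half of undrugged patients flagged per measure, even with the baseline exemption. The remaining outputs could reveal a fall, but none gives the number of patients per cohort with low readings. The change is worth making because it is cheap and brings blood pressure into line with pulse and temperature. The gap does not undermine the primary safety endpoint.

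**What to change.** In SAP 9.3.3, add low-side rows for systolic and diastolic pressure, with cut-offs set by the sponsor before unblinding. Present high and low values separately, as for pulse rate and temperature, and apply the same criteria to the listing flag. State that most extreme change for vital signs is reported as both minimum and maximum change, as SAP 5.5 defines them. The cost is a few table rows and some SAP wording; the readings are already collected, so no new data are needed.
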